Adverse events will be monitored throughout the study (e.g. infection, lead migration). Lead migration will be defined as loss of efficacy that could not be remedied by reprogramming and confirmed radiologically.⁵⁶ Baseline testing will be performed either prior to SCS trial or a minimum of two weeks following removal of SCS trial leads and prior to SCS implant. During outcome assessments, the spinal cord stimulator will remain active and any medications that can impact autonomic testing will be discontinued prior to each test.

Assessments of pain will be made with the numeric rating scale (NRS) for each of the time points. The patient will be contacted at 5 and 11 months to set up in-person assessment appointments. At this time, the NRS will be used. If the NRS is ≥ 3 the principal investigator will be notified and the patient will have an appointment for a SCS assessment prior to the 6 and 12 month assessment. Neuropathic symptoms will be monitored with the Neuropathy Symptoms and Change (NSC) scale at 6 months and 12 months to assess impact on neuropathic pain (figure).⁶² Patient Health Questionnaire (PHQ9) will be assessed at baseline, 6 months and 12 months to monitor for the presence and severity of depression. A body mass index (BMI) and Hemoglobin A1C (HgA1C) will be done at baseline and at 12 months. The presence of allodynia and/or hyperalgesia will be monitored throughout the course of the study with the modified Leeds Assessment of Neuropathic Symptoms and Signs (S-LANSS).⁶³ Small fiber sudomotor function with Q-SWEAT will be assessed periodically during the study (baseline, 6 months, and 12 months) (figure).^{28, 53, 58, 59, 64, 65}

Gross neurologic function will be assessed by a board certified neurologist at baseline, 6 months, and 12 months, and the neuropathy impairment score (NIS) of the lower limbs with lower limb function test (LLF) will be calculated for an objective comparative assessment.^{66, 67} EMG will be performed at baseline (partly to exclude mimickers of DPN) and at 12 months to compare nerve conduction studies (NCS) for an objective assessment of large fiber nerve function(figure).⁶⁷ Only the NCS of the lower limb will be performed with the EMG at 12 months (no needle EMG will be performed at 12 months). The Oswestry Disability Index (ODI) will be used as a gross functional assessment at each of the time points.

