Account, member, certificate or professional license numbers, health beneficiary numbers		
Vehicle identifiers and serial numbers, including license plate numbers		
Check 'None' when none of the identifiers listed above will be recorded, maintained, or shared during the conduct of this study. (exempt category 4)	 None	 None

Data Analysis

Power analyses and study endpoints are not required for minimal risk research, pilot or feasibility studies.

No statistical information. *If checked, please explain:* feasibility study.

Power Statement:

This is a feasibility study and so a power analysis was not performed.

Data Analysis Plan: Demographic data will be reported with descriptive statistics, including means with SD's for continuous data and percentages and counts for categorical data. Assuming a normal distribution, two-sided paired *t* tests and analysis of covariance (ANCOVA) will be used to compare means in VAS/NRS pain scores, NSC, ODI, NIS, LLF, and S-LANSS scores at the corresponding time points as the primary endpoints(figure). In addition, two-sided paired *t* tests and analysis of covariance (ANCOVA) will be used to compare means for amplitudes (mA) and conduction velocity (m/s) on NCS with EMG at baseline and 12 months post-implant. The secondary endpoints will be assessed with two-sided paired *t* tests and analysis of covariance (ANCOVA) for latency (min) and sweat output ($\mu\text{L}/\text{cm}^2$) on Q-SWEAT and arbitrary perfusion units on Laser Doppler flowmetry (p.u.) at baseline, 6 months, and 12 months post-implant.

Endpoints:

[figure not shown]
Primary: Changes in VAS/NRS, NSC, ODI, NIS, LLF, and S-LANSS.

Secondary: Changes in latency (min) and sweat output ($\mu\text{L}/\text{cm}^2$) on Q-SWEAT, arbitrary perfusion units (p.u.) on Laser Doppler flowmetry, and amplitudes (mA) and conduction velocity (m/s) on NCS when compared to baseline. Changes in BMI, HgA1C and PHQ9 scores when compared to baseline.

FIGURE

Quantitative Assessment of Painful Diabetic Peripheral Neuropathy after High Frequency Spinal Cord Stimulation: (QUANT) HF10 Study

REFERENCES:

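### The text lists the NSC, one of six primary measures, at 6 and 12 months without naming baseline; unless the schedule figure adds that visit, change from before implant cannot be computed as a paired score difference

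*Combined protocol and SAP*

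**What the plan says.** Under Study Design and Methods, Outcome Assessments, the NSC sentence reads: "Neuropathic symptoms will be monitored with the Neuropathy Symptoms and Change (NSC) scale at 6 months and 12 months". The sentence ends with a pointer to the study figure. The next sentence schedules the PHQ9 and does name baseline, along with months 6 and 12.

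Under Data Analysis, the Endpoints section states: "Primary: Changes in VAS/NRS, NSC, ODI, NIS, LLF, and S-LANSS". The Data Analysis Plan uses two-sided paired t tests and ANCOVA to "compare means in VAS/NRS pain scores, NSC, ODI, NIS, LLF, and S-LANSS scores at the corresponding time points as the primary endpoints(figure"), which again points to the figure. It does not list those time points in words.

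For other measures the same plan names the reference visit. For nerve conduction it will "compare means for amplitudes (mA) and conduction velocity (m/s) on NCS with EMG at baseline and 12 months post-implant". The Q-SWEAT measures and "arbitrary perfusion units on Laser Doppler flowmetry (p.u.) at baseline, 6 months, and 12 months post-implant" are handled likewise. The secondary endpoint line also says that its changes are relative to baseline. The primary line does not.

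**The concern.** A paired t test needs two scores from the same patient. In a single-arm before-and-after study, the pair that bears on treatment is one score before implant and one after. The NSC sentence gives explicit visits, and both fall after implant. A coordinator who works from the text, and sees baseline written into the next sentence for the PHQ9, could reasonably conclude that no baseline NSC is required.

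What is at stake is whether one primary measure can be analysed as change from the untreated state. A pre-implant score cannot be collected once the device is in place, so each patient implanted without one is a permanent loss for that comparison.

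**Working it through.** There is no plan figure to reproduce: the documents give no effect size, SD, alpha level or power for the NSC. The check is a comparison of schedules, followed by a count.

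**Step 1. Text schedule of each primary measure (Outcome Assessments)**

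| Primary measure | Visits in the text | Baseline named or allowed? |
|---|---|---|
| VAS/NRS | "Assessments of pain will be made with the numeric rating scale (NRS) for each of the time points" | Allowed |
| NSC | 6 and 12 months | Not named |
| ODI | "The Oswestry Disability Index (ODI) will be used as a gross functional assessment at each of the time points" | Allowed |
| NIS | Baseline, 6 and 12 months | Named |
| LLF | Baseline, 6 and 12 months, with the NIS | Named |
| S-LANSS | Throughout the study, visits not specified | Allowed |

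The NSC is the only one of the six with an explicit visit list that leaves baseline out.

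**Step 2. Does any other visible text supply the visit?**

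- The baseline-testing sentence in Outcome Assessments gives a window: before the stimulation trial, or at least two weeks after removal of the trial leads and before implant. It names no instruments.
- The Methods text on baseline testing gives its purpose as excluding confounders. It does not mention the NSC.
- The Data Analysis Plan names baseline for nerve conduction, Q-SWEAT and Laser Doppler, but not for the primary measures.

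No visible text places the NSC at baseline.

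**Step 3. Count the pairs.** Target accrual under Subject Information is 20, so 20 is the most that any count can reach.

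| NSC pair | Text schedule alone | If baseline is added |
|---|---|---|
| Baseline and 6 months | 0 | up to 20 |
| Baseline and 12 months | 0 | up to 20 |
| 6 and 12 months | up to 20 | up to 20 |

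**Step 4. What the remaining pair measures.** Write Y0, Y6 and Y12 for a patient's NSC scores before implant, at 6 months and at 12 months. The one available difference is

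Y12 − Y6 = (Y12 − Y0) − (Y6 − Y0).

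It is the difference between two changes from baseline. Without Y0 neither change can be recovered from it, and any change already present at month 6 and still present at month 12 cancels out. An ANCOVA with baseline NSC as covariate also needs Y0. The plan does not say which covariates its ANCOVA will use.

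**The case against.** The strongest objection is the figure. Both the NSC sentence and the primary analysis sentence refer to it, and it is not shown in the copy reviewed. The text relies on it elsewhere too: the time points for the NRS and ODI are never listed as a set. The figure may be the full schedule and may list a baseline NSC. The narrative is also incomplete in other respects. Outcome Assessments does not mention Laser Doppler flowmetry, which the Data Analysis Plan places at baseline, or the foot TcPO2 and composite autonomic score that the exclusion criteria need. This objection stands in part. A reader might infer that the trial omits a baseline NSC; the documents do not establish that. But the NSC sentence is not silent. It lists visits, and if the figure adds baseline then text and figure disagree on a primary measure.

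A second objection concerns the instrument. Its name includes the word change, and the documents do not describe its scoring. A reader might infer that no change from before implant could be captured at all. That goes too far, because the scale may ask patients to recall change. Even so, recalled change would not replace the planned paired comparison of mean scores.

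Third, the primary endpoint line names no reference visit. Change from baseline is the natural reading, because the hypothesis is improvement in patients treated with the device, but it is a reading and not a statement. This supports naming the visit.

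Fourth, the study is a feasibility study: "This is a feasibility study and so a power analysis was not performed". That explains the missing power analysis. It does not explain a primary change measure whose starting value is not scheduled in the text.

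**Conclusion.** The point holds in conditional form. If the text is followed and the figure does not add baseline, no patient has a pre-implant NSC score, the only pair is 6 versus 12 months, and neither a paired difference from baseline nor a baseline-adjusted ANCOVA can be computed for that measure. If the figure does list baseline, the fault is confined to the text. Both cases assume that change in the primary line means change from before implant.

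The size is one of six primary measures with no baseline visit named in the text. The other five are unaffected.

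Two further inferences are tempting and should not be drawn. One is a figure for lost power. Every input would have to be assumed, including the share of any NSC change reached by month 6, and the loss could then be anything from none to complete. The other is that the Background shows how much NSC change would be missed. Its remarks on immediate and delayed response concern peripheral nerve function. They give no time course for symptom scores on the NSC.

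**What to change.** 1. Check the NSC sentence in Outcome Assessments against the schedule figure.
2. Amend that sentence so that the NSC is collected at baseline as well as at months 6 and 12, with the baseline score taken in the existing pre-implant window. Make the figure match.
3. State in the Data Analysis section (Data Analysis Plan and Endpoints) that change in NSC is measured from baseline.

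The cost is one questionnaire at an existing pre-implant visit plus short text edits. If the figure already lists a baseline NSC, only the text edits are needed. The change affects data collection and wording, not treatment. It should be made promptly, because it cannot supply a baseline score for a patient who has already been implanted without one.

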Our hypothesis is that patients with painful DPN will have improvements in sensory examination and the improvements will predominantly be in small fiber nerve function. In addition, these improvements may be objectively assessed with small fiber sudomotor testing (Q-SWEAT) as patients with length dependent diabetic peripheral neuropathy have been shown to have sudomotor dysfunction along with progressive sweat gland denervation.^{58, 59} The changes in Q-SWEAT will be an objective marker of small fiber nerve function and the proposed mechanism is through increases in perfusion of the peripheral nerves secondary to vasodilation induced by high frequency spinal cord stimulation. As the HF10 SCS leads are placed at the level of the thoracic segments, it is unlikely to result in any improvements in hand symptoms. Also, SCS would be unlikely to improve upper extremity symptoms in DPN because upper extremity symptoms in DPN are usually related to superimposed mononeuropathies (median neuropathy at the wrist or ulnar neuropathy at the elbow).⁶⁰

Patients with DPN frequently have large nerve fiber involvement as well as the small nerve fiber involvement that will be assessed with Q-SWEAT. Large nerve fiber function can be assessed with nerve conduction studies.

The proposed improvements in peripheral nerve function may occur in both an immediate (days to months) and delayed (months to years) response. Some of the more proximal nerve fibers may be in an area of penumbra where chronic neuropraxia (dysfunctional but still intact) is causing the impairments. With improved perfusion of these fibers, recovery of function may happen more quickly (days to months). In the more distal nerves fibers, the deficits are more likely related to chronic axonotmesis (axonal damage with nerves intact) or neuronotmesis (both axonal and nerve damage), which would likely take more reperfusion time to demonstrate improvements (months to years) with deficits related to axonotmesis. The pain improvement effects of HF10 SCS are sustained with long term data of success with HF10 SCS being demonstrated up to 24 months.⁶¹

Study Design and Methods

Methods: *Describe, in detail, the research activities that will be conducted under this protocol:*

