Resources: *Describe the available resources to conduct the research (personnel, time, facilities, mentor commitment, etc.):*

1. Clinical research coordinator to aid in implementation of the study
2. Periodic testing (Q-SWEAT and Laser Doppler flowmetry) will be performed in the Clinical Research Unit (CRU)

(1a) This is a multisite study involving Mayo Clinic and non Mayo Clinic sites. *When checked, describe in detail the research procedures or activities that will be conducted by Mayo Clinic study staff.*

(1b) Mayo Clinic study staff will be engaged in research activity at a non Mayo Clinic site. *When checked, provide a detailed description of the activity that will be conducted by Mayo Clinic study staff.*

Subject Information

Target accrual is the proposed total number of subjects to be included in this study at Mayo Clinic. A "Subject" may include medical records, images, or specimens generated at Mayo Clinic and/or received from external sources.

Target accrual: 20 patients over the course of a 2 year enrollment period (3 years in total for completion of study).

Subject population (children, adults, groups): Patients with the FDA approved indication of medically intractable painful DPN age 18 and over that are appropriate surgical candidates and without severe autonomic neuropathy or psychiatric comorbidity that would preclude SCS implant.

Inclusion Criteria:

- ≥ 18 years of age
- Type 2 diabetes mellitus
- Refractory predominantly lower extremity neuropathic pain for > 1 year
- Presence of length dependent peripheral neuropathy on sudomotor testing (Q-SWEAT)
- Completed spinal cord stimulation trial with 40% or greater pain reduction from baseline
- Failed medication trials or contraindication to gabapentinoid medications (gabapentin, pregabalin) and/or serotonin/norepinephrine reuptake inhibitors (tricyclic antidepressant (TCA) or duloxetine or venlafaxine)
- Average pain score on a numeric rating scale of ≥ 5 (with 0 representing no pain and 10 the worst pain imaginable)
- Appropriate surgical candidate for SCS⁵⁶

Exclusion Criteria:

- Severe Autonomic Neuropathy as measured by the composite autonomic scoring scale (10 point scale) with a score ≥ 7 ^{52, 64}
- History of sympathectomy⁵²
- Uncontrolled arterial hypertension (Systolic Blood Pressure >160)^{26, 27}
- Baseline Foot TcPO₂ < 10 mmHg to exclude patients with severe peripheral arterial disease^{28, 29}
- Hemoglobin A1c $> 8\%$ ^{68, 69}

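### NIS and LLF are examiner-scored primary endpoints described as objective, but nothing in the protocol keeps earlier scores or pain and test results from the neurologist before scoring.

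*Combined protocol and SAP*

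**What the plan says.** Under Study Design and Methods, Outcome Assessments: "Gross neurologic function will be assessed by a board certified neurologist at baseline, 6 months, and 12 months". The same sentence says that NIS of the lower limbs with LLF "will be calculated for an objective comparative assessment".

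The Data Analysis section lists NIS and LLF among the primary endpoints, to be analysed with two-sided paired t tests and ANCOVA. Follow-up is compared with the same patient's baseline, and no control arm is described. Target accrual is 20. The section gives no power analysis, alpha, effect size or SD, because this is a feasibility study.

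Three other statements bear on what the examiner could know:

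- On the stimulator: "During outcome assessments, the spinal cord stimulator will remain active".
- If the NRS at the 5- or 11-month contact is 3 or more, "the principal investigator will be notified and the patient will have an appointment for a SCS assessment".
- The inclusion criteria require at least 40% pain reduction during the stimulation trial.

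The protocol nowhere mentions blinding, masking, an independent examiner, or withholding earlier scores or results from the person who scores.

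**The concern.** NIS and LLF depend on a clinician's judgement at the bedside. An examiner who has the baseline score, or knows how much pain relief the patient reports, can be drawn toward a change that fits. The direction is predictable, since the study hypothesis is that nerve function in the legs improves. In a randomised comparison with masked assessors, much of such a shift would fall on both arms and cancel. Here it would go straight into the mean change from baseline and could not be told apart from a treatment effect.

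At stake is how a positive NIS or LLF result can be read. These are the primary endpoints that come from the neurologist's examination, so they carry much of the claim about nerve function as distinct from pain. Calling them objective invites the reader to take them as protected from expectation, and the protocol describes no such protection.

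**Working it through.** **What the text establishes.** The whole document was read for any statement about who scores, what that person sees, and in what order.

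| Question | What the protocol says |
|---|---|
| Who scores NIS and LLF? | A board certified neurologist; whether it is the same one at each visit is not stated |
| Are they primary? | Yes (Data Analysis) |
| Is there a concurrent comparison? | None described; change from baseline only |
| Are earlier NIS/LLF scores withheld? | Not stated |
| Are pain, symptom or test results withheld? | Not stated |
| Does the neurologist receive them? | Not stated; the only described flow of pain data is to the principal investigator |

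The supportable statement is that no safeguard is described. It is not that a breach occurs.

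**How much a shift could matter (illustration).** The plan has no figure to reproduce. Input from the protocol: n = 20, two-sided paired t test. Assumptions not in the protocol: alpha 0.05, a true mean change of zero, and a systematic scoring shift of d standard deviations of the paired change.

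The test statistic then follows a noncentral t distribution with n − 1 degrees of freedom and noncentrality d√n. With T so distributed and c the 97.5% point of the central t on n − 1 degrees of freedom, the rejection probability is P(T > c) + P(T < −c). For n = 20, √n = 4.472.

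| d | d√n | Rejects toward improvement | Rejects toward worsening | Total |
|---|---|---|---|---|
| 0 | 0 | 2.5% | 2.5% | 5.0% |
| 0.1 | 0.447 | 6.2% | 0.9% | 7.1% |
| 0.2 | 0.894 | 13.4% | 0.3% | 13.6% |
| 0.3 | 1.342 | 24.7% | 0.1% | 24.7% |

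Entries are rounded separately, so rows may not add exactly.

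If 20% of patients were lost (an assumption; 20 × 0.8 = 16), the totals for d = 0.1, 0.2 and 0.3 would be 6.6%, 11.7% and 20.3%.

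These are rates for one test of one endpoint. The excess over 5% lies wholly on the improvement side. The protocol gives nothing from which d could be estimated.

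**The case against.** The case against making much of this has five parts.

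1. *Silence is not evidence.* A reader might infer that the neurologist does see earlier scores and pain results. The documents do not say so, and the one pain result they route to anyone goes to the principal investigator. This stands: the point is a missing safeguard, not a described practice.

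2. *The word may be harmless.* Objective may mean only an examination finding as opposed to patient report. That is a fair reading and makes part of the complaint semantic. It does not supply the missing condition of scoring.

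3. *Withholding results hides little.* Every participant is a known responder to the stimulation trial, baseline precedes implant, and the stimulator is active at later visits. A live examination may reveal pain status in any case. This largely stands. The remedy acts on anchoring to recorded values; it cannot remove the examiner's general expectation or the patient's own expectation in sensory responses.

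4. *The illustration follows mechanically from an assumed shift.* Also correct. A reader might take 25% as the estimated false-positive rate of this study, and the documents do not support that.

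5. *Nerve conduction and sweat testing.* The protocol also calls these objective ("to compare nerve conduction studies (NCS) for an objective assessment of large fiber nerve function"; "The changes in Q-SWEAT will be an objective marker of small fiber nerve function"), and a reader might extend the concern to reading tracings with the visit known. The documents do not say who reads them, whether recordings are stored, or whether values are marked by hand. As instrument recordings they probably leave less room for the reader. Coded re-reading would also create a second set of baseline values, since Q-SWEAT decides eligibility and the baseline EMG serves partly to exclude mimickers, and there is no rule for discrepancies. The extension is not established.

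After these concessions, the point about NIS and LLF remains: primary, examiner-scored, compared only with baseline, and with no stated limit on what the examiner sees first.

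**Conclusion.** The point holds for NIS and LLF as a low-cost improvement, not as a defect that undermines the study. It rests on three things in the text: the neurologist scores these endpoints, they are primary and tested as within-patient change with no control arm described, and no masking or withholding is stated.

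The size cannot be determined. Under the assumptions listed, a shift of 0.1 to 0.3 SD of the change takes the false-positive rate of one paired test from 5% to between 7% and 25%. Both the true shift and the share of it that withholding results would remove are unknown. Feasibility status explains the absence of a power analysis; it does not stop two-sided tests on these scores from being read as evidence of improved nerve function.

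It would go too far to say that the scores are known to be biased, that the remedy makes the examination blind, or that the nerve conduction and sweat endpoints share the problem to the same degree.

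**What to change.** Add to Outcome Assessments that, at each visit, the neurologist records and locks NIS and LLF before seeing:

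- NIS or LLF scores from earlier visits;
- pain and symptom scores from that visit;
- Q-SWEAT, NCS or laser Doppler results.

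Where the neurologist also administers a symptom scale, NIS and LLF are scored first. Results can be released once the scores are locked, so clinical use of them is not prevented.

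State in the protocol and the report that masking is only partial: the implant and responder status are known, and patient expectation in sensory responses remains. If the lock is not adopted, drop the word objective for NIS and LLF and report unmasked scoring as a limitation.

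Coded reading of NCS and Q-SWEAT recordings is optional. It applies only if tracings are stored and measured by hand, and it would need a rule for discrepancies with the baseline values already read for eligibility and diagnosis.

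The cost is a few sentences of protocol text, a fixed order within the visit, and some coordination, for which the Resources section lists a study coordinator. The sample size and analysis do not change, and the same neurologist can do the scoring.

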Patients with intractable neuropathic lower extremity pain related to DPN that fulfill inclusion and exclusion criteria (see below) will be considered for participation in this prospective feasibility study. Baseline testing will be performed to exclude confounding factors that may affect outcomes (figure). All patients that are candidates for SCS undergo a spinal cord stimulation trial as part of standard clinical care with all of the FDA approved indications. If the patient is deemed a candidate and complying with this standard clinical practice, the patient will undergo a HF10 SCS (Nevro Senza®) trial lasting up to 14 days with an external stimulator to determine short term response.⁵⁶ Patients with 40% or greater pain reduction from baseline will be eligible to proceed to permanent implantation.⁵⁶ Patients with HF10 SCS will receive 30 μ s pulses delivered at 10,000 Hz with amplitude adjusted to optimal analgesic response. Programming will occur postoperatively and as needed based on patient feedback in standard clinic visits.⁵⁶ At 6 month follow-up, paresthesia mapping will be performed during the programming visit in which the subthreshold SCS will be temporary increased during a 10 minute protocol to a perceived level to determine the dermatomal stimulation pattern with the SCS lead placement.

Implant Procedures

The SCS implant will follow standard clinical practice for these FDA approved indications. Two percutaneous leads will be placed in the posterior spinal epidural space under radiographic guidance and attached to either an external stimulator (trial phase) or a subcutaneously implanted impulse generator (IPG). The distal tip of one lead will be placed at the top of the T8 vertebral body and the second lead tip will be placed at the mid T9 vertebral level for maximal electrode coverage at the T9/T10 junction.⁵⁶ A subcutaneous pocket will be created using standard surgical techniques for placement of an IPG. The leads, anchored to the supraspinous fascia, will be tunneled to the pocket site and connected to the IPG. Intraoperative impedance testing will be performed to ensure electrical integrity.⁵⁶

Outcome Assessments

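### Q-SWEAT both selects patients and serves as a change-from-baseline endpoint in a single group; if one test does both jobs, regression to the mean can look like small-fibre recovery

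*Combined protocol and SAP*

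**What the plan says.** - **Entry** (Subject Information, Inclusion Criteria): "Presence of length dependent peripheral neuropathy on sudomotor testing (Q-SWEAT"). No cut-off, site, date or repeat-test rule is given.
- **Schedule** (Outcome Assessments): "Small fiber sudomotor function with Q-SWEAT will be assessed periodically during the study (baseline, 6 months, and 12 months"). No separate screening Q-SWEAT is described in the text; the schedule figure is not available to us.
- **Role and timing of baseline testing** (Methods; Outcome Assessments): "Baseline testing will be performed to exclude confounding factors that may affect outcomes", so baseline tests help to select patients. On timing: "Baseline testing will be performed either prior to SCS trial or a minimum of two weeks following removal of SCS trial leads", and before implant.
- **Endpoint and test** (Data Analysis): "Secondary: Changes in latency (min) and sweat output" on Q-SWEAT, compared with baseline. "The secondary endpoints will be assessed with two-sided paired" t tests and ANCOVA. No significance level is stated.
- **Interpretation** (Background): "The changes in Q-SWEAT will be an objective marker of small fiber nerve function". Aim 2 rests on this measure.
- **Size and design**: "Target accrual: 20 patients over the course of a 2 year enrollment period". One group; no control arm is described.

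**The concern.** A single Q-SWEAT value is partly the patient's stable sudomotor function and partly measurement and day-to-day variation. Requiring an abnormal result favours people whose variation happened to run in the abnormal direction that day. At the next test that part is drawn afresh, and the group mean moves back towards the mean of everyone tested. A control arm chosen in the same way would move equally and cancel the shift; here there is none.

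At stake is the reading of Aim 2. A change that arises from selection could be reported as objective evidence of small-fibre recovery and carried into the design of a later trial. The plan mentions no retest reliability, duplicate baseline or allowance for regression to the mean.

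**Working it through.** The plan gives no power, variance or error-rate figure, so there is nothing to reproduce. The check asks what the planned test does when nothing has changed.

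**Inputs.** From the documents: n = 20, one group, two-sided paired t test. Assumed: a 5% significance level (so 2.5% nominal in the direction of improvement), retest correlation r, and share f of tested candidates who qualify. Neither r nor f is in the documents.

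**Step 1: qualifying test is the baseline.** For a bivariate normal with entry limited to the worst fraction f, the expected change with no treatment effect, in baseline SDs, is

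shift = (1 − r) × φ(z_f) / f.

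Example, f = 0.5 and r = 0.7: 0.3 × 0.798 = 0.24 SD. False improvement below is the share of 20,000 simulated trials with a significant improvement and no true change; repeat runs differ by about one percentage point.

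| f | φ(z_f)/f | shift, r = 0.8 | shift, r = 0.6 | false improvement, r = 0.8 to 0.6 |
|---|---|---|---|---|
| 30% | 1.159 | 0.23 | 0.46 | 37% to 67% |
| 50% | 0.798 | 0.16 | 0.32 | 20% to 37% |
| 70% | 0.497 | 0.10 | 0.20 | 10% to 17% |
| 90% | 0.195 | 0.04 | 0.08 | 4% to 6% |

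**Step 2: does ANCOVA help?** At f = 0.5 and r = 0.7 the paired t test gives 28%. A single-group ANCOVA with centred baseline estimates the same 0.24 SD and gives 30%. Without a second group there is nothing to adjust against.

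**Step 3: separate baseline.** If the analysis baseline is a different pre-implant test from the qualifying one, the expected shift is 0.00 SD and false improvement about 2.5% at every f and r tried.

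**Step 4: trimming at the severe end.** The exclusion of composite autonomic scores of 7 or more may remove the worst Q-SWEAT results. If it removed the worst 10% (an assumption), then at r = 0.7:
- f = 0.5: 0.24 falls to 0.17 SD, and 28% to about 17%;
- f = 0.7: 0.15 falls to 0.09 SD, and 13% to 7%;
- f = 0.9: 0.06 falls to about 0 SD, and 5% to 2.5%.

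Removing the worst 20% at f = 0.9 slightly reverses the bias.

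**Step 5: entry on a pattern.** The criterion is a length-dependent pattern, so selection may act on a distal-minus-proximal contrast. With correlation ρ between the two sites' error-free values, the distal shift at f = 0.5 is (1 − r) × 0.798 / √(2(1 − ρr)). At r = 0.7:
- ρ = 0: 0.239 / 1.414 = 0.17 SD;
- ρ = 0.5: 0.239 / 1.140 = 0.21 SD.

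False improvement at the distal site is then about 15% to 22%. The proximal site shifts equally the other way, and a two-site average does not shift.

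**Step 6: can a correction be used as a pass/fail test?** Subtracting (1 − r) × (mean of all candidates tested − baseline mean of enrolled patients) brings false improvement back to 2.2% to 2.6% when r is right. If r is wrong by 0.3 at f = 0.5, the error is 0.3 × 0.798 = 0.24 SD. True r 0.9 corrected with 0.6 gives false worsening in 63% of trials; true 0.6 corrected with 0.9 leaves 22% false improvement. It therefore suits a sensitivity analysis over a range of r, not a test at one value.

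**The case against.** The strongest reply is that the bias needs the qualifying test to be the baseline, and the text never says it is. Resources places the periodic Q-SWEAT in the Clinical Research Unit, baseline testing may follow the stimulation trial, and the medical-record review reaches back to 01/01/2015. An earlier clinical sudomotor result could therefore be the qualifier. This stands, and it makes the finding conditional.

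It can also be said that candidates already have intractable painful neuropathy, and Background says that length-dependent diabetic neuropathy comes with sudomotor dysfunction. Most might then qualify, which leaves little selection. Background also describes progressive degeneration and sweat gland denervation, which would push change the other way. Both are fair, but neither is quantified in the plan.

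Finally, Q-SWEAT is a secondary endpoint in a feasibility study without a power analysis. That limits the weight of the point. It does not remove it, because the plan still specifies hypothesis tests on this endpoint and calls its change an objective marker.

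A reader might infer that any Q-SWEAT gain in this trial will be spurious, or that the false-improvement rate is around two thirds. The documents support neither. The first requires a link between the two tests that is not stated; the second is one corner of an assumed range.

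**Conclusion.** The point holds as a conditional one. If the qualifying Q-SWEAT is also the analysis baseline, which the single described pre-implant test suggests but the text does not state, regression to the mean can look like small-fibre recovery. Neither planned analysis separates the two.

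False improvement runs from about 4% to 67% over the assumed range (r 0.6 to 0.8, 30% to 90% qualifying, n = 20, 5% two-sided). It is near nominal if almost everyone qualifies or the severe end is trimmed. It may appear only at distal sites. With a separate baseline it disappears. The point bears on Aim 2 and the Q-SWEAT endpoints alone, not on the listed primary endpoints.

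**What to change.** 1. **Separate the two tests where possible.** State which Q-SWEAT qualifies a patient. Where a clinical sudomotor result already exists, use it for eligibility. In every patient, use the Clinical Research Unit Q-SWEAT as the analysis baseline, whatever its value. Report how many patients had separate tests.
2. **Where one test must serve both purposes,** keep the planned test and prespecify a sensitivity analysis for those patients, by site and by measure (latency, sweat output). Subtract (1 − r) × (mean of all candidates tested − baseline mean of enrolled patients) from the observed change, for r = 0.6 to 0.9.
3. **Limit the claim.** Describe a Q-SWEAT change under Aim 2 as improvement beyond regression to the mean only if it holds across that whole range; otherwise report it as an uncontrolled change. The low end of r may over-correct, so a negative corrected value should not be read as worsening.

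**Cost.** No extra test is needed. The Q-SWEAT values of all candidates tested, including those not enrolled, must be kept, which the plan does not now describe. The Q-SWEAT result may look less favourable. The analysis protects only if the true r over 6 to 12 months lies within the range shown.
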